Protocol & Statistical Analysis Plan for:

Increasing Surveillance Rates for Hepatocellular Carcinoma Among Cirrhotic Patients

University of Pennsylvania

[name]

NCT#04248816

v. 7/20/21

Approved: 7/23/21

Increasing surveillance rates for hepatocellular carcinoma among cirrhotic patients

Abstract

This is a 3-arm pilot randomized controlled trial applying behavioral economic approaches (opt-out framing and financial incentives) to encourage patients with liver cirrhosis to complete regular surveillance ultrasounds which may allow for earlier diagnosis of and better outcomes for hepatocellular carcinoma (HCC).

Study Instruments

A sub-sample of 134 patients (approximately 67 from each intervention arm) will be called to complete a questionnaire over the phone 6 months after initial outreach was mailed. The subjects will confirm their eligibility (e.g. that they had received outreach about HCC surveillance) and be asked about their experience with and perception of the impact of HCC surveillance outreach.

Group Modifications

Subjects in the usual care arm will not receive a post-outreach phone questionnaire since these subjects will not be sent outreach materials.

Method for Assigning Subjects to Groups

Subjects will be randomly assigned Study ID numbers and then randomized to one of three study arms in a 1:2:2 ratio using a computer-generated randomization algorithm. The randomization will occur in three batches 3 months apart and will be stratified by batch. The research coordinator will record the randomization assignments on a master list which will be maintained on a password protected computer. The research staff will assemble the mailings based on this master list. For the post-intervention phone interviews, a proportion of the 134 subjects will be randomly selected from each batch of randomized participants mailed outreach, based on batch size, using STATA. For example, if batch 1 contained 142 patients out of the total 480 randomized to one of the intervention arms, then 29.6% of the 134 subjects (equaling approximately 40) will be randomly selected from batch 1 to be called for the interview.

Administration of Surveys and/or Process

134 subjects will be randomly selected for the follow-up interview with the goal of completing 30 interviews. We anticipate the post outreach interview to take approximately 15 minutes to complete over the phone. The research staff will make no more than three attempts to speak directly with the subject. We originally anticipated reaching about 50% of patients via phone call, however, after contacting the first sample of batch 1 patients we found the response rate to be much lower. Based on this, we have increased our sample from 60 subjects to 134 subjects based on a 25% response rate and taking into account already completed interview outreach.

Data Management

Information about study subjects will be kept confidential and managed according to the requirements of the Health Insurance Portability and Accountability Act of 1996 (HIPAA). Source documents are maintained in PennChart. No source documents will be printed or maintained in paper form at the study site. Data from PennChart will be recorded in Penn Medicine's REDCap system. The investigator and study team will have access to PHI within PennChart and REDCap. We will label all PHI within REDCap as identifiable information so that de-identified exports are possible. All reports that include identifiable information will

be stored on the Innovation Center secure drive, maintained behind the UPHS firewall. Direct identifiers will be maintained on RedCap until manuscript publication in case additional chart review is needed for confirmation of results. Once data analysis and manuscripts have been published, direct identifiers will be deleted from RedCap and the de-identified database will be stored on the Innovation Center secure drive.

Objectives

1.1 Objectives

Aim 1: To evaluate if a proactive approach to facilitated HCC surveillance outreach that incorporates opt-out framing increases participation as compared to usual care.

Aim 2: To evaluate if an unconditional incentive informed by behavioral economics increases response to facilitated HCC surveillance outreach.

1.2 Primary outcome variable(s)

The primary outcome is the proportion of subjects who have a surveillance abdominal ultrasound in the six-month period after the study begins.

1.3 Secondary outcome variable(s)

The secondary outcome is the proportion of subjects who have any hepatocellular carcinoma surveillance in the six-month period after the study begins.

Additional variables include the etiology of cirrhosis, demographic and socioeconomic characteristics of subjects who participate, differences by provider/specialty, number of clinic visits, differences among MyPennMedicine users and non-users, as well as exploratory qualitative data regarding experience with outreach. Additionally, we will track the percentage of HCC surveillance images that are abnormal, result in follow-up imaging, result in a diagnosis of HCC and follow-up care, and incidental findings during imaging.

Background

There is a substantial burden of HCC-related morbidity and mortality: The age-adjusted incidence rates of HCC have tripled in the US since the 1980s due to the burden of hepatitis C virus (HCV) and the epidemic of non-alcoholic fatty liver disease (NAFLD). The overwhelming majority of HCC in the US occurs in the setting of cirrhosis. The age group most affected by cirrhosis and HCC are baby boomers given that HCV is the leading risk factor for cirrhosis and HCC, followed by NAFLD, hepatitis B virus, and alcohol. The current burden of HCC translates to more than 30,000 new HCC diagnoses every year, with greater than 20,000 HCC-related deaths annually. The incidence of HCC is projected to increase over the next 10-20 years.

Early diagnosis of HCC dictates survival: The American Association for the Study of Liver Diseases (AASLD) recommends biannual HCC surveillance for all patients with cirrhosis using an abdominal ultrasound. These guidelines seek to maximize early diagnosis of HCC which leads to earlier detection and improved survival because early-stage HCC is curable, with 70% 5-year survival compared to 5% in advanced disease.

HCC surveillance rates are suboptimal: Despite longstanding published guidelines for HCC surveillance, adherence is low, with surveillance rates ranging from 15-30% in the US. Two RCTs have tested interventions to increase HCC surveillance, including electronic reminders for primary care providers and mailed reminders (with or without navigators), but neither has been scalable, produced durable responses, or increased surveillance rates above 50%.

HCC surveillance rates at HUP are low: Several thousand patients with advanced liver disease (cirrhosis) receive medical care at the University of Pennsylvania Health System, largely at the outpatient clinic managed by the hepatologists within the Division of Gastroenterology, and the transplant hepatologists through the multi-disciplinary Liver Transplant program. Despite slight differences in the definition of compliance, the percentage of cirrhotic patients receiving outpatient care at HUP who were compliant with HCC surveillance remains limited.

Statistical Considerations

1.1 Power and sample size

Approximately 700 potentially eligible subjects will be identified in the initial batch via a data abstraction by the Clarity database. Approximately 160 newly eligible patients will be identified in the second batch via a data abstraction by Clarity conducted 3 months after the initial pull. Based on preliminary review, we estimate that 30% of patients complete screening outside of Penn or will be ineligible based on chart review, leaving approximately 600 eligible patients. As such, we anticipate we will have enough patients to enroll at least 600 subjects (and randomize in a 1:2:2 ratio to usual care, opt-out, and incentive arms). We estimate a base return rate for the usual care arm to be 10%. We will consider a meaningful increase in response rate to be 13 percentage points for the opt-out arm as compared to usual care (23%), and 13 percentage points for the incentive arm as compared to the opt-out arm (36%). This will be sufficient sample size using a two-tailed chi-squared test of proportions with 80% power and a Type 1 error rate of .025, accounting for two pairwise comparisons with Bonferroni correction (.05/2 = .025).

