1.2 Data analysis

We will conduct a chi-square test of proportions analysis using Stata to compare arm 2 to arm 1 and arm 3 to arm 2 separately using intent-to-treat protocol for the ultrasound completion and any HCC surveillance imaging completion. As exploratory analyses, we will evaluate response by age, gender, race/ethnicity, income at the level of zip code, etiology of cirrhosis, and provider/specialty. We will also evaluate differences in response rate among MyPennMedicine users and non-users and scheduling modality (MyPennMedicine vs. call). Additionally, we will evaluate the percentage of HCC surveillance images that are abnormal, result in follow-up imaging, result in a diagnosis of HCC and follow-up care, and incidental findings during imaging between the study arms. Analysis will be conducted at least six months after initial outreach.

Study Design

[figure not shown]

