1.1 Design

Randomized: This is a 3-arm randomized controlled trial. Patients with cirrhosis will be identified from eligible patients at the Penn Gastroenterology clinic via medical records query. Their providers will be contacted with the opportunity to opt-out on behalf of the patients. Approximately 490 eligible patients identified in the initial batch will be randomized 1:2:2 into a usual care arm and 2 intervention arms using a computer-generated randomization algorithm (Figure 1). Three months after the initial batch, approximately 110 newly eligible patients will be identified and randomized as described above (Figure 1). Three months after the second batch, a third and final data pull will be completed to identify any remaining patients meeting study criteria. Randomization will be stratified by batch. The research coordinator will record the randomization assignments on a master list which will be maintained on a password protected computer. The usual care arm (120 patients) will receive standard of care. The first intervention arm (240 patients) will involve facilitated outreach and opt-out framing, and research staff will send a letter to those patients encouraging them to get a surveillance ultrasound and include an order

slip for them to get it done at a health system facility. The second intervention arm (240 patients) will be the same process but will also offer an unconditional incentive of \$20 compensation.

Blinding: The investigators will be blinded to the randomization assignment. The research staff will be unblinded. The blinding may be broken for clinical care purposes.

Figure 1. Batch Accrual and Randomization Diagram

Study duration

We anticipate conducting chart review for two months, mailed outreach and reminder follow-up for two months, waiting for completion of screening for an additional four months, conducting the sub-sample survey for one month, and data analysis and manuscript compilation for 3 months. Thus, we anticipate this project to last 12 months. We anticipate screening ultrasounds to take approximately 1 hour. For the subsample of participants completing the follow-up survey, we would expect the phone call to take approximately 15 minutes.

Resources necessary for human research protection

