Intervention - Patients will either receive standard of care (usual care group), receive a letter encouraging them to get a surveillance ultrasound plus an order slip for the procedure (opt-out), or receive the letter and order slip plus an unconditional incentive of \$20 (incentive). Patients then have the option to complete the ultrasound. A second data pull will be used to determine ultrasound completion at 2 months after initial outreach for all patients in the study. If they have not completed screening within 2 months from initial outreach, the research staff will send a reminder similar to the original messaging and including the order slip. A reminder will not be sent if the patient has a future ultrasound scheduled or a different screening modality is now recommended. A final data pull will be used to determine ultrasound completion at 6 months from initial outreach for all patients in the study. Some patients may have their screening completed outside of Penn and View-only Care Everywhere encounters that have been downloaded into the patient's chart may be reviewed for this information. Care Everywhere will not be used to request clinical information for research purposes.

Sub-sample Questionnaire - A sub-sample of 134 patients will be called to complete a questionnaire over the phone 6 months after initial outreach was mailed. The subjects will confirm their eligibility (e.g. that they had received outreach about HCC surveillance) and be asked information about their qualitative experience with the outreach materials and approach. We anticipate these questionnaires to take no more than 15 minutes to complete over the phone. The research staff will make no more than three attempts to speak directly with the subject. Interviews will be recorded and transcribed.

Analysis Plan

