1.2 Data analysis

We will conduct a chi-squared test of proportions analysis using Stata to compare arm 2 to arm 1 and arm 3 to arm 2 separately using intent-to-treat protocol for the ultrasound completion and any HCC surveillance imaging completion. As exploratory analyses, we will evaluate response by age, gender, race/ethnicity, income at the level of zip code, etiology of cirrhosis, and provider/specialty. We will also evaluate differences in response rate among MyPennMedicine users and non-users and scheduling modality (MyPennMedicine vs. call). Additionally, we will evaluate the percentage of HCC surveillance images that are abnormal, result in follow-up imaging, result in a diagnosis of HCC and follow-up care, and incidental findings during imaging between the study arms. Analysis will be conducted at least six months after initial outreach.

Qualitative analysis of the post-intervention phone interviews will be conducted using NVivo. This will include thematic analysis of patient experience with the intervention and screening process.

Analysis will be conducted by blinded members of the research team at least 6 months after the mailings have been sent.

Data Confidentiality

Paper-based records will be kept in a secure location and only be accessible to personnel involved in the study. Computer-based files will only be made available to personnel involved in the study through the use of access privileges and passwords. Wherever feasible, identifiers will be removed from study-related information. Audio and/or video recordings will be transcribed and then destroyed to eliminate audible identification of subjects.

Subject Confidentiality

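### Replacing Bonferroni with Holm's step-down would raise power per primary comparison from about 81% to 88% if both planned 13-point effects are real, and gains almost nothing if only one is; an inexpensive improvement, not an error

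*Combined protocol and SAP*

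**What the plan says.** Both power sections (Statistical Considerations 1.1 and Analysis Plan 1.1) use a two-sided chi-square test with 80% power and a per-comparison error rate of .025, "accounting for two pairwise comparisons with Bonferroni correction (.05/2 = .025"). The planned rates are 10% (usual care), 23% (opt-out) and 36% (incentive).

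The Design section gives the arm sizes: "The usual care arm (120 patients) will receive standard of care", and each intervention arm has 240.

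The Objectives list two separate aims. The first is opt-out outreach against usual care. The second reads "Aim 2: To evaluate if an unconditional incentive informed by behavioral economics increases response to facilitated HCC surveillance outreach".

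The Data analysis sections say the team will "compare arm 2 to arm 1 and arm 3 to arm 2 separately using intent-to-treat protocol for the ultrasound completion", and the same sentence adds any HCC surveillance imaging as a second endpoint. They give no multiplicity rule. No step-down or other sequential procedure appears anywhere in the document.

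**The concern.** Nothing in the plan is invalid. The point is efficiency. Plain Bonferroni holds each comparison at .025 even after the other has been declared significant. Once one null hypothesis is rejected, only one is left to protect, and the 5% familywise target allows it to be tested at .05. Holm's procedure does this. It needs no assumption about how the two tests are correlated, so the opt-out arm's appearance in both comparisons is no obstacle.

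The power lost by not doing so falls in the scenario the trial was sized for, where both interventions work. There the plan misses at least one real effect in 100 − 63.2 = 36.8% of trials.

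**Working it through.** **Inputs.** Arm sizes 120/240/240 (Design 1.1). Rates 10/23/36% and per-comparison error .025, two-sided chi-square (power sections). All other rates below are assumptions.

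**The plan's own figure.** Normal approximation with pooled variance under the null:

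power = Φ{ [ |p₂ − p₁| − z·√( p̄(1 − p̄)(1/n₁ + 1/n₂) ) ] / √( p₁(1 − p₁)/n₁ + p₂(1 − p₂)/n₂ ) }, with z = 2.2414 for two-sided .025.

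- Aim 1 (10% v 23%, 120 v 240): p̄ = (12 + 55.2)/360 = .1867. The null standard error is √(.1518 × .0125) = .04356 and the alternative one is .03857. Then (.13 − 2.2414 × .04356)/.03857 = .839, so power is 79.9%.
- Aim 2 (23% v 36%, 240 v 240): p̄ = .295. The standard errors are .04163 and .04121. Then (.13 − 2.2414 × .04163)/.04121 = .890, so power is 81.3%.

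The stated 80% is reproduced.

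**Holm against Bonferroni.** The figures below come from exact enumeration of three independent binomial counts, with the uncorrected pooled chi-square and the opt-out arm shared between the tests. Holm rejects a comparison if its p ≤ .025, or if its p ≤ .05 and the other comparison's p ≤ .025.

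Power, Bonferroni → Holm:

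| Rates (%) | Aim 1 | Aim 2 | Both |
|---|---|---|---|
| 10/23/36 (plan) | 80.6 → 87.7 | 81.5 → 87.7 | 63.2 → 76.4 |
| 10/20/30 | 57.9 → 66.2 | 61.7 → 68.5 | 29.5 → 44.6 |
| 10/15/20 | 16.4 → 17.3 | 21.2 → 22.0 | 1.1 → 2.9 |
| 10/23/26 | 80.6 → 81.6 | 7.1 → 10.2 | 3.8 → 7.8 |
| 10/23/23 (opt-out only) | 80.6 → 80.8 | – | – |
| 10/10/23 (incentive only) | – | 95.2 → 95.3 | – |

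Consistency check at the plan's rates: Holm adds an Aim 1 rejection with probability .0703 and an Aim 2 rejection with probability .0615. So both = .6317 + .0703 + .0615 = .7635. At least one = .8766 + .8766 − .7635 = .9897, the same as under Bonferroni.

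**The price.** Error on the single true null when the other intervention works:

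| Rates (%) | Bonferroni | Holm |
|---|---|---|
| 10/23/23 | 2.5% | 4.3% |
| 10/36/36 | 2.5% | 5.1% |
| 10/10/23 | 2.4% | 4.7% |
| 10/10/36 | 2.4% | 4.9% |

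The slight excess over 5% comes from the chi-square approximation. Bonferroni shows a similar excess over its nominal .025 (.0253 at 10/36/36). With no effect in any arm, the chance of any false rejection is the same under both rules: 4.6% at 10%, 4.7% at 23% and 4.8% at 36%.

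**Agreement with intervals.** The plan names no interval, so a 97.5% Wald interval for the risk difference is assumed. At the plan's rates Holm adds a rejection in .0703 + .0615 = 13.2% of trials. In .0261 + .0590 = 8.5% of all trials the added rejection has an interval that includes zero. That is .0851/.1318 = 65% of the added rejections, and .0590/.0615 = 96% of those for Aim 2.

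**The case against.** **Bonferroni meets its target.** It delivers the 80% the plan asked for, no passage requires both aims to succeed, the abstract calls the trial a pilot, and the chance of at least one success does not change. That is correct, and it is why this is a recommendation and not a correction. The two aims are nonetheless stated separately, and the sample size assumes both effects.

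**Timing.** This is the strongest objection. The survey section reports that calls to the first sample of batch 1 patients had already been made, and those calls are scheduled for 6 months after mailing, when the primary outcome window closes. Batch 1 is planned as about 490 of 600 patients (82%); the interview-sampling example would make it 142 of 480 (30%). In addition, "A second data pull will be used to determine ultrasound completion at 2 months after initial outreach for all patients in the study", and "The research staff will be unblinded". A significance rule loosened at this stage carries a real credibility cost. Against that, investigators are described as blinded, and "Analysis will be conducted by blinded members of the research team at least 6 months after the mailings have been sent". The Design section also lets blinding be broken for clinical care, so the team must establish who still qualifies to decide. If no one does, Bonferroni should stay.

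**Narrow benefit.** Holm gains much only when both effects are sizeable. At 10/15/20% it adds about one point per comparison. This stands.

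**Intervals.** Most of the added rejections would sit beside a 97.5% interval that includes zero. This also stands, and the report has to say so.

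**Secondary outcome.** The analysis sentence covers both endpoints, "for the ultrasound completion and any HCC surveillance imaging completion", so placing the secondary outcome outside Holm could look like a new choice. It fits the plan's own count of two comparisons, but the plan gives no error rate for the secondary tests.

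**Conclusion.** The point holds as an inexpensive improvement. If both planned 13-point effects are real, Holm raises power by 7.0 points for Aim 1 and 6.2 for Aim 2, and the chance of confirming both by 13.2 points, at the same nominal 5% familywise error and with no extra patients. If one intervention is inert, it adds at most 0.2 points in the cases checked and brings the error on the inert one to between 4.3% and 5.1%.

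These figures assume the planned arm sizes and an uncorrected chi-square test. With a continuity correction (simulated), power moves from 76.4% to 83.9% for Aim 1 and from 78.7% to 85.2% for Aim 2: a similar gain at a lower level. The team should weigh the gain against the higher error on an inert arm and the late timing.

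**What to change.** Make the change by a dated amendment, decided by investigators and analysts who have seen no outcomes by arm, and before any unblinded analysis.

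1. In both Data analysis sections, add: *The two primary-outcome comparisons (arm 2 v arm 1, arm 3 v arm 2) will be tested with Holm's procedure at familywise alpha .05: the smaller p-value at .025 and, only if significant, the other at .05. The secondary-outcome comparisons are outside this procedure.*
2. In both power sections, add: *The sample size was set conservatively at the Bonferroni .025; the analysis uses Holm's procedure.*
3. Report risk differences with confidence intervals, and state that a 97.5% interval may include zero for a comparison rejected only at the .05 step.

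The sample size stays as it is. The cost is a few sentences in four sections and the amendment, plus the downsides above: the higher error on an inert intervention, possible conflict between test and interval, and the credibility cost of a late change. If the team declines, or cannot show that the decision is made blind to outcomes by arm, it should keep Bonferroni, which remains valid.
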